9.4 Study Population

Both Parts:

Eligible patients will have a diagnosis of COVID-19 with or without respiratory symptoms. No gender and/or ethnicity restrictions will apply. Each patient should meet all the inclusion and none of the exclusion criteria in order to be eligible for the study.

Part 1:

The study population will include 1 or 2 cohorts of approximately 9 patients (up to approximately 18 patients) randomized in a ratio of 2 active to 1 placebo. Patients will have a primary diagnosis of COVID-19. Patients may be hospitalized, inpatient in a research unit, or seen in an outpatient clinic or in a home care setting. At-home assessments may be performed using a combination of remote digital monitoring of patient-reported information, home visits by qualified research team staff (include nurses or medical assistants), and telehealth evaluation by study investigators. Implementation of the home-based outpatient assessment, including remote digital monitoring and telehealth evaluation, may include use of a digital application.

Part 2:

Part 2 will enroll up to approximately 150 patients receiving at least one dose of study treatment. Patients may be hospitalized, inpatient in a research unit, or seen in an outpatient clinic or in a home care setting.

If a patient begins treatment but is not confirmed to have a positive SARS-CoV-2 result from the pre-treatment stool sample by the central lab, the patient will remain on randomized treatment and will continue study assessments.

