9.6 Exclusion Criteria

Patients will be excluded from the study if one or more of the following criteria are applicable:

1. At the time of randomization, patients requiring ICU admission or patients with severe respiratory insufficiency requiring mechanical ventilation or with rapid worsening of respiratory function leading to expectation for mechanical ventilation or ICU admission.
2. Evidence of rapid clinical deterioration or existence of any life-threatening co-morbidity or any other medical condition that, in the opinion of the investigator, makes the patient unsuitable for inclusion.
3. Patients who, at the time of enrollment, are not in a clinical condition compatible with the oral administration of the study drug.
4. Patients with serum alanine transaminase (ALT) or aspartate transaminase (AST) > 3 times upper limit of normal (ULN) detected within 24 hours prior to randomization or other evidence of severe hepatic impairment (Child-Pugh Class C).
5. Patients with an estimated GFR (eGFR) ≤ 30 mL/min/1.73m² (based on CKD-EPI formula) at screening.
6. Patients with a history of hypersensitivity or allergy to any component of the study drug.
7. Enrollment in another concurrent clinical interventional study, intake of an investigational drug within 30 days prior to randomization, or intake of an investigational drug for COVID-19 within 3 months prior to randomization. Drugs approved under a US Food and Drug Administration Emergency Use Authorization are not considered investigational under this exclusion.
8. Pregnant or lactating women or women with a positive pregnancy test (urine or serum).

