6.1. Demographics

A summary of demographics and baseline information will be presented by treatment group and overall. The demographic characteristics consist of age, sex, race, and ethnicity. The baseline characteristics consist of the WHO severity score as reported in [Appendix 16.2](#), loose or watery stool on Day 1, abdominal symptom(s) on Day 1, stool test for SARS-CoV-2 by RT-qPCR on Day 1, stool test for bacteria or parasites at Screening (local laboratory) and COVID-19 vaccination(s) prior to Screening.

Age (years) will be summarized using descriptive statistics. The number and percentage of subjects will be presented for each of the following variables and its associated categories:

- Age (<65, ≥65)
- Sex (Male, Female)
- Race (White, African American, Asian, American Indian or Alaska Native, Native Hawaiian or Other Pacific Islander, Other),
- Ethnicity (Hispanic or Latino, Not Hispanic or Latino),
- WHO severity score (ordinal categorical scores of 1 to 7)

- Loose or watery stool on Day 1 (Yes, No) as collected on the Diarrhea Clinical Assessment at Randomization eCRF
- Abdominal symptom(s) on Day 1 (Yes, No)
- Stool test for SARS-CoV-2 by RT-qPCR on Day 1 (Positive, Negative)
- Stool test for bacteria or parasites at Screening (Positive, Negative)
- COVID-19 vaccination(s) prior to Screening (Yes, No)

Subject demographic and baseline characteristics will also be presented in a listing.

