8.3.6. Time to nasopharyngeal viral clearance assessed by RT-PCR

Only subjects with positive test on Day 1 will be included in this analysis.

Time to nasopharyngeal viral clearance is defined as the time in days from the first dose of study treatment to the first nasopharyngeal RT-PCR sample negative for SARS-CoV-2. Subjects without nasopharyngeal clearance will be censored using the same rules as described for the primary efficacy endpoint in [Section 8.1](#).

A summary table will include the number and percentage of subjects achieving and not achieving the first nasopharyngeal viral clearance up to each post-first dose study visit (Days 4, 8, 15, 22, 29, 36, and 43) by treatment group. For each study visit, only subjects with available assessment at the visit or having a negative nasopharyngeal test before the visit will be included in the summary and counted in the denominator for the percentages.

Time to nasopharyngeal viral clearance will be analyzed using the same time to event methods as described for the analysis of the primary endpoint in [Section 8.1.1](#).

8.3.7. Proportion of subjects requiring hospitalization and duration of hospitalization from first dose through Day 43

Hospital admissions and dates of stay will be captured on the Hospitalizations eCRF.

Summary table containing the proportion of subjects requiring any hospitalization and the duration of hospitalization will be presented for each treatment group. A subject will be considered as requiring hospitalization if the subject has at least one hospital admission with an admission date between the first dose date and the Day 43 follow-up visit date (inclusive). The duration of hospitalization in days will be calculated by taking the sum of the duration (discharge date – admission date + 1) for each hospitalization.

9. Safety Analysis

Safety analyses will be conducted on safety data collected through the Day 43 follow-up visit for all randomized subjects and will be included as part of the Day 43 Final Analysis for the main CSR. All safety analyses will be performed using the SAF set and will be presented separately for Part 1 and Part 2 of the study unless otherwise specified.

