10.4. Summarization of genotypic resistance analysis data

Nasopharyngeal swabs and stool samples will be collected and stored for possible genotypic resistance analysis. The summary results will be provided when data become available.

11. Interim Safety Analysis

The interim safety data review for Part 1 and 2 of the study will be performed by the DMC (see [Section 12](#), below). Data to be reviewed includes subject disposition, demographics, medical history, concomitant medications, study drug Exposure and compliance, adverse Events, safety clinical laboratory and vital signs. The DMC will be unblinded to study data and will operate under a DMC charter. Blinded and unblinded PPD Biostatisticians will produce and provide tables, listings, and figures requested by the DMC.

Part 1 will enroll approximately 9 hospitalized subjects. After treatment is concluded for all 9 subjects, the DMC will review the safety data and determine if the study may proceed to Part 2 or if additional subjects are needed to assess tolerability of the study drug. If additional subjects are needed, approximately 9 more subjects will be enrolled in Part 1, and then the DMC will meet again after all subjects are treated to determine if the study may proceed to Part 2. Due to the relatively small number of subjects in Part 1, the decision for DMC review of Part 1 will be based on medical judgment of niclosamide tolerability compared to placebo and will not require specific statistics.

For Part 2, the planned interim safety data review will occur when 50 subjects have been randomized and completed the 2-week treatment period. The outcome from the DMC to be delivered to the sponsor will be: (1) continue as planned; (2) pause enrollment and undertake further evaluation of safety; or (3) recommend that the study be terminated due to safety concerns. No rigid statistical stopping rules will be used to make these decisions. While the DMC statistician may perform statistical analyses to examine adverse trends in safety, such as excess deaths and SAEs in the active arm, the decision to recommend a pause in enrollment or termination of the study will be reached by clinical consensus of the DMC.

No formal interim analysis for efficacy is planned to stop the study early for benefit or futility.

12. Data Monitoring Committee (DMC)

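### SAP 8.3.7 shows patients already in hospital at first dose as not requiring hospitalization unless readmitted, and its duration formula does not yield hospital days from first dose through Day 43

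*SAP*

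**What the plan says.** The heading of SAP 8.3.7 sets the window for both parts of the endpoint: "Proportion of subjects requiring hospitalization and duration of hospitalization from first dose through Day 43". For the proportion, a subject qualifies with "at least one hospital admission with an admission date between the first dose date and the Day 43 follow-up visit date (inclusive". For duration, the SAP prescribes "taking the sum of the duration (discharge date – admission date + 1) for each hospitalization".

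Both documents expect some patients to be in hospital when dosing starts. Protocol 9.4 says: "Patients may be hospitalized, inpatient in a research unit, or seen in an outpatient clinic or in a home care setting". Exclusion 1 in Protocol 9.6 is aimed at the need for intensive care or ventilation ("At the time of randomization, patients requiring ICU admission or patients with severe respiratory insufficiency requiring mechanical ventilation", or an expectation of either), not at ordinary inpatients. SAP section 11 goes further for the first cohort: "Part 1 will enroll approximately 9 hospitalized subjects". SAP 6.1 plans to tabulate baseline "WHO severity score (ordinal categorical scores of 1 to 7"; on the scale in SAP 16.2, scores 3 to 7 are hospitalized states.

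SAP 8.3 assigns this endpoint to the FAS. SAP section 4 makes the default denominator every subject in the arm within the analysis set. Section 8.3.7 does not override that, gives no rule for stays that began before first dose, and is not mentioned in SAP section 14.

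**The concern.** The proportion uses a new-admission rule for the numerator and everyone dosed for the denominator. Someone admitted the day before dosing who stays in hospital for weeks is reported as not requiring hospitalization. The figure is neither the share of patients who were in hospital during the window nor the rate of new admission among those who could have one.

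The duration rule has a separate fault. The heading promises days from first dose through Day 43, but the formula runs from admission to discharge with no cut at either end. Which stays count as each hospitalization is not defined either. Depending on the reading, the table mixes in days that treatment could not have influenced, or drops days that it could.

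Hospitalization is a named secondary endpoint (Protocol 8.2, SAP 3.2.2), so readers will take both numbers at face value.

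**Working it through.** The documents state no hospitalization rate, duration or power for this endpoint, so there is no plan figure to reproduce. The check applies the two rules as written.

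**Proportion.** Let h be the share of subjects admitted before the first-dose date and still in hospital at first dose, and q the new-admission rate in the rest. Neither is in the documents: q = 10% is assumed, h is varied, and readmissions of baseline inpatients are set to 0.

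- SAP rule: (1 − h) × q
- Any hospital stay in the window: h + (1 − h) × q
- New admissions among those at risk: q

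| h | SAP rule | Any stay in window | At-risk rate |
|---|---|---|---|
| 10% | 0.90 × 10% = 9.0% | 10% + 9.0% = 19.0% | 10% |
| 25% | 0.75 × 10% = 7.5% | 25% + 7.5% = 32.5% | 10% |
| 50% | 0.50 × 10% = 5.0% | 50% + 5.0% = 55.0% | 10% |
| 100% | 0 × 10% = 0% | 100% | no one at risk |

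The last row is what Part 1 would show if SAP section 11 is literally true, all were admitted before the first-dose date and none was readmitted.

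**Effect on a comparison.** If both arms share the same h, the ratio of proportions is unchanged but the difference shrinks by (1 − h). Rates of 10% and 5% with h = 50% appear as 5.0% and 2.5%, a difference of 2.5 points instead of 5. Randomization is stratified by age and sex only (Protocol 9.1.2), so h can differ between arms by chance. With q = 10% in both arms, shares of 40% and 60% would show 6% and 4% with no treatment effect.

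**Duration.** The SAP's study-day rule (section 4) has no Day 0. Take a stay from Day -5 to Day 10, that is, admission 5 days before and discharge 9 days after the first-dose date.

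- Formula as written: 9 + 5 + 1 = 15 days
- Days inside the window: Days 1 to 10 = 10
- Pre-dose days: 15 − 10 = 5

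There are two readings of which stays are summed:

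1. All recorded stays: 15 days, for a subject whom the same table lists as not requiring hospitalization. For any stay that ends by Day 43, the excess equals the days from admission to first dose.
2. Only stays that meet the admission-date rule: this stay contributes nothing, and the 10 on-study days are lost.

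The heading's definition gives 10. Neither reading does.

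**Other rules in the same SAP.** Section 8.2.6 (new stool positivity) is restricted to subjects negative on Day 1, which is an at-risk denominator. Section 8.3.2 counts any supplemental oxygen given in the window, whenever it began. Section 10.3 uses an admission-date rule but labels the result as new hospitalization or rehospitalization. Section 8.3.7 has neither the at-risk denominator nor that label.

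**The case against.** Counting only new admissions is a legitimate choice, because an admission before first dose cannot be a treatment outcome. Keeping the whole FAS follows the SAP's general rule. Randomization equalizes the inpatient share in expectation, so the table is diluted but not biased. SAP 8.3.1 also tabulates WHO scores at baseline and each visit, which shows who is in hospital at those times. All of this stands, and it limits the importance of the point. It does not rescue the label or the denominator, and visit-level scores supply neither hospital days nor an at-risk admission rate.

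A reader might infer three stronger things that the documents do not support:

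- That baseline inpatients can never be events. They can: a readmission by Day 43 qualifies, Protocol 10.7.2 collects readmission dates, and an admission on the first-dose date itself also counts.
- That a planned research-unit stay starting on Day 1 would be counted as a hospitalization. Protocol 9.4 lists research-unit inpatients separately from hospitalized patients, and nothing says that such stays are recorded as hospital admissions.
- That pre-dose days are certainly included. The duration sentence follows directly after the definition of a qualifying admission, so the second reading above is natural. Under it the error runs the other way.

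On days after Day 43, SAP section 8 confines efficacy analyses to data collected through that visit. This probably limits the overrun, but the formula does not say so and gives no rule for a stay still open then.

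**Conclusion.** The point holds. As written, 8.3.7 reports baseline inpatients who are not readmitted as not requiring hospitalization, and lowers the absolute proportion in line with their share. At an assumed 10% admission rate in the others, with no readmissions, an inpatient share of 10% to 50% gives 9% to 5%. The true share is not in the documents, so the size is illustrative. The duration result does not depend on any assumed rate: under either reading, the formula fails to give hospital days from first dose through Day 43 for a patient admitted before dosing.

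No systematic bias between arms is shown. Section 8.3.7 specifies a summary table and names no test, and the primary analysis and sample size are unaffected. It should be corrected because the stated rule gives a wrong result, and the correction is cheap.

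**What to change.** Amend SAP 8.3.7 as follows:

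- **Proportion.** Report subjects with at least one new admission through the Day 43 visit among FAS subjects not in hospital at first dose. Show baseline inpatients on separate rows, including how many were readmitted. State how an admission on the first-dose date is classified.
- **Duration.** For every FAS subject, sum for each stay the days from the later of admission and first dose to the earlier of discharge and the Day 43 visit, inclusive. Subjects with no hospital day in the window contribute zero. End stays still open at Day 43 on that date, and state how an in-hospital death closes a stay.
- **Consistency.** Apply the same limits to the day counts in SAP 8.3.2 (oxygen) and 8.3.5 (intensive care), which are built on the same uncut formula.

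This takes a few sentences and no new data, since admission and discharge dates are already on the Hospitalizations eCRF. The only statistical cost is a smaller denominator for the proportion. With 75 per arm in Part 2 (150 randomized 1:1), an assumed inpatient share of 25% would remove about 19 per arm (75 × 0.25 = 18.75). Those subjects remain visible on their own rows and in the duration summary.

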9.1. Adverse Events

Adverse events (AEs) will be coded using the Medical Dictionary for Regulatory Activities (MedDRA) Version 23.0 and classified by system organ class (SOC) and preferred term (PT) for all summaries.

The period of observation for AEs extends from the time the subject gives informed consent until the subject completes the Day 43 follow-up visit. AEs will be classified as pre-treatment AEs and treatment emergent adverse events (TEAEs) and are defined as follows:

- A pre-treatment event is any event that meets the criteria for an AE/SAE and occurs after the subject signs the informed consent form but before receiving the first administration of study drug.
- A TEAE is defined as an AE occurring or worsening on or after the date of first dose of study drug.

A treatment-related AE will be defined as related if causality is definitely, probably, or possibly related. AEs where the causality is missing will be assumed to be related in table summaries.

TEAEs leading to study drug discontinuation will be identified as TEAEs with a study drug action taken of “Drug Withdrawn”. TEAEs leading to death will be identified as TEAEs with an outcome of “Death Related to Adverse Event”.

The severity of AEs (serious and non-serious) will be graded in accordance with the investigator’s clinical judgement as follows:

- Mild: The AE does not interfere in a significant manner with normal functioning but may be an annoyance.
- Moderate: The AE produces some impairment of functioning but is not hazardous to health but is uncomfortable and/or an embarrassment. These events are usually ameliorated by simple therapeutic measures.
- Severe: The AE produces significant impairment of functioning or incapacitation and is a hazard.

AEs with missing severity will be assumed to be severe in table summaries.

Details for imputing missing or partial start and/or stop dates of AEs are described in [Appendix 16.3](#).

All summaries of AEs will be based on treatment-emergent adverse events (TEAEs) in the safety set. The following summaries of TEAEs will be provided by treatment group:

- An overall summary of TEAEs including the number of TEAEs and the number and percentage of subjects with any of the following: TEAEs, study drug related TEAEs, TEAEs by maximum severity, TEAEs leading to study drug discontinuation, TEAEs leading to death, serious TEAEs, and study drug related serious TEAEs.
- TEAEs (by SOC and PT)
- Study Drug-Related TEAEs - by SOC and PT
- TEAEs by Maximum Severity – by SOC and PT

- TEAEs leading to study drug discontinuation – by SOC and PT
- AEs leading to death – by SOC and PT
- Serious TEAEs – by SOC and PT
- Study Drug-Related Serious TEAEs – by SOC and PT

For the above summaries by SOC and PT, each subject is counted once within each unique category. For the summary by maximum severity, subjects who experience the same event several times, with different severity levels, will only be counted with the maximum severity. AEs will be sorted in descending order of frequency of SOC based on the total of all treatment groups. Within each SOC, AEs will be sorted in alphabetical order of preferred terms.

All AEs, including pre-treatment AEs and TEAEs, will also be presented in a listing.

9.2. Clinical Laboratory Evaluations

Safety laboratory tests include chemistry and hematology on Days 1, 8, 15, 29, and 43 and will be performed by a central laboratory. All summaries will be based on the units provided by the central laboratory; no conversion will be made.

Summary tables displaying observed values and changes from baseline will be presented for numeric clinical laboratory tests by treatment group for subjects in the Safety set. Changes from baseline to each scheduled post-baseline visit (Days 8, 15, 29, and 43) will be presented. Box-and-whisker plots will also be displayed for each laboratory test at baseline and each scheduled post-baseline visit by treatment group.

All safety laboratory data will be included in separate listings and all test values outside the normal range will be flagged.

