Stool samples and nasopharyngeal swabs will be collected in the hospital or clinic or at patient's home, according to written instructions using a pre-labeled patient's kit and shipped to a central laboratory for RT-qPCR analysis of the endpoints related to viral RNA. At screening, the sample will be collected for testing at the local laboratory of viral RNA to determine eligibility. Samples that are obtained in the outpatient setting will be collected by appropriately trained and qualified personnel, for example, a home-visiting medical assistant, or by the patient after the patient receives adequate training that has been documented by qualified personnel.

10.7.4 *Safety and Laboratory Assessments*

- Stool infection analysis at the local laboratory at screening. Clostridium difficile toxin, Salmonella, Shigella, Yersinia, Plesiomonas Campylobacter, and intestinal parasites are recommended tests, but the specific bacteria or parasites to be tested can be based on local standard of care testing.
- Safety (SAEs and AEs)
- Central laboratory testing will include complete blood count (CBC), blood urea nitrogen (BUN), blood sugar, electrolytes (sodium, chloride, potassium, and bicarbonate [HCO₃]), alkaline phosphatase, AST, ALT, lactate dehydrogenase (LDH), total bilirubin, serum creatinine, C-reactive protein, and fecal calprotectin.
- Any other laboratory assessment may be conducted at the local laboratory for the physician's safety assessment according to the local practice and patient's clinical needs.

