12.5 Analysis of Safety Variables

The primary endpoint of Part 1 is summarization of safety (AEs, clinical laboratory results, and vital signs) comparing the niclosamide arm to the placebo arm.

The TEAEs, SAEs, and AEs will be presented for each treatment arm in terms of number of AEs and their incidence by SOC and preferred term (PT) using MedDRA. Analyses will be provided also by severity and relationship to the treatment.

Laboratory tests will be presented using descriptive statistics at each available visit.

Additionally, the frequency of subjects reporting an abnormal or abnormal clinically significant laboratory value at each available visit will be presented for each laboratory parameter.

12.6 Interim Safety Analysis for Study Continue/Pause Decision Part 1

The interim safety analysis for Part 1 will be performed by the DMC (see [Section 12.9](#) below). Due to the relatively small number of subjects in Part 1, the decision for DMC review of Part 1 will be based on medical judgment of niclosamide tolerability compared to placebo and will not require specific statistics.

12.7 Interim Safety Analysis Part 2

The interim safety analysis for Part 2 will be performed by the DMC (see [Section 12.9](#) below). The DMC will be unblinded to study data and will operate under a DMC charter. The planned interim analysis will occur when 75 patients have been enrolled and completed the 2-week treatment period. The outcome from the DMC to be delivered to the sponsor will be: (1) continue as planned; (2) pause enrollment and undertake further evaluation of safety; or (3) recommend that the study be terminated due to safety concerns. No rigid statistical stopping rules will be used to make these decisions. While the DMC statistician may perform statistical analyses to examine adverse trends in safety, such as excess deaths and SAEs in the active arm, the decision to recommend a pause in enrollment or termination of the study will be reached by clinical consensus of the DMC.

The chairperson of the DMC will be apprised of SAEs and other important safety events in real time and may elect to convene an ad hoc DMC meeting at any time.

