- o) Proportion of subjects with treatment-emergent adverse events (TEAEs) leading to study drug discontinuation.
- p) Serious adverse events (SAEs) coded by system organ class (SOC) and preferred term (PT) using the Medical Dictionary for Regulatory Activities (MedDRA).
- q) Clinically significant changes in laboratory measurements.
- r) Clinically significant changes in vital sign measurements.

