All subject data collected at scheduled and unscheduled visits, excluding data collected in the daily diary, will be presented in individual subject data listings. Dates will be shown in subject listings as they have been recorded. Data listings will be sorted by treatment group, subject identification number, date/time and visit where applicable. The treatment group (randomized) as well as subject's sex and age will be stated on each listing where applicable. Unless otherwise stated, data listings will be based on all subjects randomized. When no data are available for a table or listing, an empty page with the title will be produced with suitable text (e.g., "There are no records for this table/listing.").

Unless otherwise specified, baseline will be defined as the last non-missing assessment prior to or on the date that the first dose of treatment is taken. For subjects who are randomized, but not treated, the baseline will be defined as the last non-missing assessment prior to or on the date of randomization. Assessments from both scheduled and unscheduled visits will be used to determine baseline. The date of first and last dose will be collected on the End of Treatment eCRF.

Study day will be calculated relative to the first dose date:

- Day 1 is defined as the first dose date
- Assessments before the first dose date: Study Day = Assessment Date – First Dose Date
- Assessments after the first dose date: Study Day = Assessment Date – First Dose Date +1

Summaries or analyses by study visit will be based on data collected at scheduled visits (i.e., nominal visits as collected on eCRF) and data from unscheduled visits will not be included. Efficacy analyses for time to viral clearance or clinical improvement will include data from both scheduled and unscheduled visits. Laboratory treatment emergent summaries will also include data from both scheduled and unscheduled visits.

A two-sided hypothesis test will be used at a significance level of 0.05 for comparison between the niclosamide and the placebo group for the primary efficacy analysis. All other statistical analyses will also be performed using a two-sided hypothesis test at a nominal significance level of 0.05. No adjustment for Type I error will be made for multiple comparisons. Models will include stratification factors, age (<65 years or ≥65 years) and sex (female or male), unless an insufficient amount of data exists where convergence or the analysis cannot be performed.

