9.2.2 Chemistry

The following laboratory tests will be included: blood urea nitrogen (BUN), blood sugar, electrolytes (sodium, chloride, and bicarbonate [HCO₃]), alkaline phosphatase, AST, ALT, lactate dehydrogenase (LDH), total bilirubin, serum creatinine, C-reactive protein, and fecal calprotectin.

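### SAP 9.2 leaves out the protocol's table of abnormal and clinically significant laboratory values and omits potassium, and endpoints (q) and (r) have no dedicated analysis

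*SAP*

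**What the plan says.** **Protocol.** Section 12.5 sets out two laboratory presentations. The first is descriptive statistics by visit. The second is that "the frequency of subjects reporting an abnormal or abnormal clinically significant laboratory value at each available visit will be presented for each laboratory parameter". Section 8.2 makes clinically significant laboratory changes and clinically significant vital sign changes secondary safety endpoints, and says that all secondary endpoints compare the two arms. Section 10.7.4 gives the central laboratory panel, including "electrolytes (sodium, chloride, potassium, and bicarbonate". Section 12.1 leaves the detailed methods to the SAP.

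**SAP.** Section 3.2.2 keeps both endpoints: (q), "Clinically significant changes in laboratory measurements", and (r), the vital-sign counterpart. The laboratory analysis in Section 9.2 is this: "Summary tables displaying observed values and changes from baseline will be presented for numeric clinical laboratory tests by treatment group", box plots for each test at each visit, and listings in which "all test values outside the normal range will be flagged". The chemistry list in Section 9.2.2 has "electrolytes (sodium, chloride, and bicarbonate" and no potassium. Section 9.3 plans values and changes for vital signs, plus a listing. Section 4 says that "Laboratory treatment emergent summaries will also include data from both scheduled and unscheduled visits". Section 14, on changes to the planned analysis, covers only the stool-scale types, the half-day imputation and the absence of censoring for last watery stool.

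**The concern.** The SAP keeps an endpoint defined by individual clinically significant changes but plans only distributional summaries and listings for the data behind it. No laboratory or vital-sign table in Section 9 says how many subjects in each arm had an abnormal or clinically significant result.

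That matters because a laboratory safety signal usually shows as a few patients crossing a limit, and the natural comparison is a count per arm. Laboratory results and vital signs are also part of the Part 1 primary endpoint. There, about 9 patients randomized 2:1 give about 6 on niclosamide and 3 on placebo.

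If the SAP is programmed exactly as written, a presentation that the protocol promised will be missing from the main report, as will the tables for one collected analyte. Nothing in the SAP will tell a reader that this was a decision.

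**Working it through.** The plan gives no figure to reproduce, so the check sets the sections side by side.

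**1. Laboratory presentations**

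| Output | Protocol 12.5 | SAP 9.2 |
|---|---|---|
| Descriptive statistics by visit | Yes | Yes |
| Frequency of abnormal or abnormal clinically significant values, by parameter and visit | Yes | No |
| Box plots | Not mentioned | Yes |
| Listings with out-of-range flags | Not mentioned | Yes |

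Of the protocol's two presentations, the SAP keeps one and omits one. The listing flag marks values outside the normal range. It does not mark clinical significance, and 9.2 gives neither a criterion nor a data source for that judgement.

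**2. Endpoints against analyses**

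- Endpoint (q): no count or percentage by arm in SAP 9.2.
- Endpoint (r): no count or percentage by arm in SAP 9.3. Protocol 12.5 promises the frequency table for laboratory values only, so this gap rests on endpoint (r) and not on a dropped protocol table.

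**3. Panel items**

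- Protocol 10.7.4: blood count, urea nitrogen, glucose, sodium, chloride, potassium, bicarbonate, alkaline phosphatase, AST, ALT, LDH, bilirubin, creatinine, C-reactive protein and fecal calprotectin. That is 1 + 14 = 15 items, counting the blood count as one.
- SAP 9.2.1 and 9.2.2: 1 + 13 = 14 items.
- Difference: 15 − 14 = 1, and the missing item is potassium.
- SAP Appendix 16.1, footnote 4, includes potassium, so the SAP disagrees with itself.

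**4. Unscheduled results**

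SAP Section 4 excludes unscheduled visits from summaries by visit and includes them in treatment-emergent laboratory summaries. Section 9.2 specifies no such summary. The one laboratory table that would capture an abnormal value between scheduled visits is therefore mentioned but has no content.

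**5. Declaration**

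None of these differences appears in SAP Section 14.

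**The case against.** The strongest reply is that the information will still come out.

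- **Adverse event tables.** Protocol 13.3 requires clinically significant laboratory abnormalities to be recorded in the eCRF and keeps only those without clinical significance out of adverse event recording. The significant ones should therefore reach the treatment-emergent event tables in SAP 9.1, which are by arm. This stands in part. Those tables are by system organ class and preferred term, not by parameter and visit. They do not cover values that are abnormal but not significant, and the SAP does not name them as the analysis of (q) or (r).
- **Extreme values.** A reader might infer that a single extreme result would vanish into a group mean. The documents do not support that: SAP Section 4 includes the minimum and maximum in every continuous summary, and 9.2 adds box plots and flagged listings. What these do not give is the number of subjects affected in each arm.
- **Intended but not written.** The Section 4 sentence suggests that a categorical laboratory summary was planned, and the table shells it mentions are not among the documents reviewed. That may explain the gap, but the SAP text still needs to define the output.
- **Potassium.** Given Appendix 16.1, this may be a transcription slip, and it does not affect endpoint (q) for the other analytes. It still needs correcting.
- **Part 1 oversight.** The DMC reviews unblinded laboratory data and decides on medical judgement without specific statistics. Its decision does not depend on the missing table.

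**Conclusion.** The point holds as an undeclared departure of the SAP from the protocol. One of two promised laboratory presentations and one of 15 panel items are missing, one summary is mentioned but not specified, and endpoints (q) and (r) have no dedicated analysis by arm.

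Some stronger readings should not be drawn. A reader might infer that endpoint (q) cannot be reported, or that it would yield no comparison of the arms. Neither follows, because the adverse event tables, the extremes and the listings remain. Nor should potassium be argued from a population defined by diarrhea: protocol version 3.0 enrols regardless of overt gastrointestinal symptoms. Potassium belongs in the list because the protocol and the SAP's own schedule say that it is measured.

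Two assumptions underlie this. The first is that protocol 13.3 means significant abnormalities are entered as adverse events, which its wording implies but does not state outright. The second is that no unseen table shell already supplies the missing counts. If one does, the correction is to the SAP text alone.

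**What to change.** 1. **SAP 9.2:** add the number and percentage of subjects with abnormal (low or high) values and with abnormal clinically significant values, by parameter, visit and arm. Say that clinical significance is taken from the assessment recorded in the eCRF.
2. **SAP 4 and 9.2:** specify the treatment-emergent laboratory summary as a count of subjects by arm over the post-baseline period, unscheduled visits included.
3. **SAP 9.3:** add a count by arm of subjects with clinically significant vital sign changes, for endpoint (r).
4. **SAP 9.2.2:** restore potassium.

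If any of the protocol's presentation is to be left out on purpose, Section 14 should say so and give the reason. A count of ALT or AST above 3 times the upper limit of normal is optional: the protocol uses that limit only for eligibility and promises no such table.

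The cost is one or two laboratory tables, a short vital-sign table and a one-word correction. No new data collection should be needed, provided that the eCRF holds the clinical-significance assessment for vital signs as well as for laboratory values.
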